12.2 Source Documents

Source data is all information, original records or clinical findings, observations, or other activities in a clinical trial necessary for the reconstruction and evaluation of the trial. Source data are contained in original source documents. Examples of these original documents and data records include (as applicable): hospital records, clinical and office charts, laboratory notes, memoranda, participant's diaries or evaluation checklists, pharmacy dispensing records, recorded data from automated instruments, copies or transcriptions certified after verification as being accurate and complete, microfiches, photographic negatives, microfilm or magnetic media, x-rays, participant files, pharmacy records, laboratory records, medical records (including electronic records) relative to the clinical trial. For this study, documents relevant to documenting and verifying inclusion and exclusion criteria, prior medical history, concomitant medications, safety labs, and assessments relevant to any AE's are pertinent.

12.3 Data Collection

Data will be collected using Electronic Data Capture (EDC). Participants will be identified by PID#; no participant personal information (PPI) is collected as part of the EDC; nor is PPI retained as part of study data. All PPI is retained at each site and controlled by the site PI.

12.4 Record Retention

It is the Investigator's responsibility to retain study essential documents as per country regulations: in the US for at least 2 years after the last approval of a marketing application in their country and until there are no pending or contemplated marketing applications in their country or at least 2 years have elapsed since the formal discontinuation of clinical development of the investigational product. The sponsor will inform the investigator/institution as to when these documents are no longer needed to be retained.

12.5 Safety and Quality Monitoring and Record Availability

Monitoring of the clinical trial will be performed by experienced monitors, who will report to the Sponsor as outlined in the Monitoring Plan.

The investigator will make study documents (e.g., ICFs, drug accountability forms) and pertinent hospital or clinic records readily available for inspection by the local IRB, the site monitors, regulatory agencies, GeneOne Life Science, Inc. or its designee for confirmation of the study data.

Participation as an Investigator in this study implies acceptance of potential inspection by regulatory authorities and applicable compliance and quality assurance offices.

12.6 Adverse event (AE) Reporting

AEs will be recorded and forwarded to regulatory agencies as required (e.g. Annual report).

12.6.1 Study Reporting Period of Adverse Events

All solicited and unsolicited adverse events are collected during the entire study period and recorded in the eCRF.

- The original SAE form must be kept at the study site. Copies (or electronic copy) will be provided to GeneOne Life Science or its representative, who will be responsible for reporting to regulatory authorities as indicated, and copy will be forwarded to the study sites IRB.

12.6.3 Notification of Serious Adverse Events

In accordance with local regulations, the Sponsor shall notify the appropriate regulatory authorities, and all participating investigators in a written safety report of any adverse experience associated with the use of the product that is both serious and unexpected. Reports of SUSARs

shall be made as soon as possible and in no event later than 15 calendar days after the Sponsor's initial receipt of the information. Written notification may be submitted on the form described above or equivalent or in a narrative format and shall bear prominent identification of its contents. Each written notification to regulatory agencies shall be transmitted to the division that has responsibility for review. In each written safety report, the Sponsor shall identify all safety reports previously filed concerning a similar adverse experience and shall analyze the significance of the adverse experience in light of the previous, similar reports. The Sponsor shall also notify the relevant regulatory authorities by telephone or by facsimile transmission of all deaths regardless of causality and any unexpected fatal or life-threatening experience associated with the use of the drug as soon as possible but in no event later than 7 calendar days after the Sponsor's initial receipt of the information. Each telephone call or facsimile transmission to regulatory agencies shall be transmitted to the division that has responsibility for review.

Follow up information to a safety report shall be submitted as soon as the relevant information is available. If the results of a Sponsor's event investigation show that an adverse drug experience not initially determined to be reportable is, in fact, reportable, the Sponsor shall report such experience in a written safety report as soon as possible, but in no event later than 15 calendar days after the determination is made. Results of investigations of other safety information shall be submitted, as appropriate, in an information amendment or annual report. In the event of death, if an autopsy is performed, a copy of the report, redacted for PHI but labeled with the PID#, should be sent to GeneOne Life Science, Inc.

The MFDS may request the sponsor to submit the sponsor's monitoring report to the laboratory for the first case reported as "SUSAR causing death".

Through this, a survey can be conducted when necessary, such as finding that the investigator does not comply with major clinical trial standards.

12.7 Study Discontinuation

GeneOne Life Science reserves the right to discontinue the study for safety or administrative reasons, including lack of enrollment, at any time. Investigational product must be returned to GeneOne, unless instructed otherwise. Document retention will follow local regulation.

13. ETHICAL CONSIDERATIONS AND ADMINISTRATIVE PROCEDURES

13.1 Clinical trial management standards and Declaration of Helsinki

The procedures specified in this protocol are the international council for harmonization of technical requirements for pharmaceuticals for human use-good clinical practice (ICH-GCP), Korean good clinical practice (KGCP) and Declaration of Helsinki.

This clinical trial will be conducted in accordance with the ethics regulations based on the Declaration of Helsinki, ICH-GCP, KGCP and related laws.

13.2 Consent of Study Participant

- 1) The investigator must give the study participant (the study participant's representative, if applicable) a sufficient opportunity to explain in detail all matters related to the clinical trial and to know all predictable results.
- 2) If consent cannot be obtained due to reasons such as lack of comprehension ability or intention expression ability of the study participant, the written consent of the representative is obtained. In this case, the consent of the representative shall not contradict the intention of the study participant. The representative of the study participant shall be the legal representative, in the order of spouse, direct continuation, and direct subordinate if there is no legal representative, but if there are several direct or direct descendants, it is determined by consultation.
- 3) The investigator must provide sufficient time for the study participant (representative, if necessary) to voluntarily decide on participation. Therefore, upon completion of the explanation, the subject (representative, if necessary) can decide whether to participate in the clinical trial in an independent space where the investigator and the investigator are not present (meaning to take time to consider it sufficiently), and the next possible visit. It is recommended to be able to make decisions in the city.
- 4) The contents agreed by the study participant (representative if necessary) must be recorded in documents.
- 5) The investigator must confirm the participation of the study participant (representative, if necessary) in the clinical trial by signing the Informed Consent Form (Attachment 1). Investigators should not perform specific tests for the sole purpose of clinical trials until consent is obtained from the study participant (if necessary, an agent).
- 6) The investigator must confirm whether the study participant (representative if necessary) continues to participate in the clinical trial at each visit after obtaining written consent.
- 7) The investigator should emphasize that the subject (representative, if necessary) has the freedom to withdraw his/her consent to participation at any time without disadvantage or loss of the original interest.
- 8) When new information is identified that may relate to the study participant (representative, if necessary) willingness to continue participating in the clinical trial, the investigator shall inform the study participant (representative, if necessary) of this information in a timely manner.

13.3 Compliance with Ethics

Clinical trials should be conducted in accordance with the clinical trial protocol (including the subject's description and consent form) approved by the Institutional Review Committee and MFDS. Clinical trials should be performed in accordance with the items described in Section 11.1.

13.4 Study Participant Safety Protection Measures

Based on the Declaration of Helsinki, the investigator must carry out the clinical trial according to Section 11.1 with the rights and welfare of the subject in mind, and all investigators and investigators must accurately understand the clinical trial protocol and perform the clinical trial in compliance with the protocol do.

The Investigators must take precautions such as sufficient education for the clinical trials personnel, and promptly respond to the occurrence of adverse reactions and perform necessary reports.

13.5 Publication of Research Findings

Publication of the results of this trial will be allowed. Any proposed presentation, abstract and/or manuscript must be made available to GeneOne at least 60 days prior to submission. GeneOne shall have fifteen (15) days for review. If GeneOne considers that material would reveal protectable intellectual property, GeneOne may request a delay in submission for a maximum of three (3) months from the date of receipt in order for patent application(s) to be filed with the United States Patent and Trademark Office and/or foreign patent office(s).

13.6 Quality Control and Reliability Assurance

Sponsors are responsible for verifying procedures and data for conducting clinical trials to protect subjects and ensure the reliability of clinical trial results.

The sponsor conducts an advance visit prior to the initiation of the clinical trial, and recruits subjects after the initiation visit. In order to ensure that clinical trials are performed in compliance with the matters described in Section 11.1, and clinical trial results can be recognized at the time of registration at home and abroad, the sponsor of the clinical trial may conduct monitoring and audit. The test manager agreed to conduct the inspection by signing this protocol.

At the monitoring visit, the sponsor will check against the supporting documentation to ensure that the clinical trial is being carried out in accordance with the approved protocol and items described in Section 11.1, and that the eCRF records are complete and clear. The investigator and the head of the clinical trial site (if applicable) must agree to and cooperate with the sponsor to directly access all relevant data and to devote time to the investigator oneself or the person concerned to discuss the problems found and related matters. .

The regulatory authority may also conduct an investigation at any time during the clinical trial or at the end of the clinical trial. In the case of inspection or investigation, the investigator (and the clinical trial site) allows the inspector and the investigator to directly access the relevant documents, and devotes the investigator himself or the person concerned to discuss the found problems and related matters and must agree and cooperate with what to do.

13.6 Approval of Clinical Trial Protocol

The clinical trials can be started after the clinical trial protocol and related documents are submitted to the MFDS and the Institutional Review Committee and approved.

13.6 Changes in Clinical Trial Protocol

Neither the investigator nor the sponsor may change the contents of this clinical trial protocol during the clinical trial without the consent of the other party. Once the test has begun, modifications should be made only in exceptional cases. Any changes to the clinical trial protocol must be signed and agreed in writing by all parties involved. Before conducting a clinical trial with the changed contents, the modified clinical trial protocol must be submitted to the MFDS and/or the Institutional Review Committee for approval.

13.6 Data and Safety Monitoring Board (DSMB)

In this clinical trial, an independent data and safety monitoring board (DSMB) is convened to evaluate the safety of subjects. The DSMB is convened at the request of investigators and sponsors, and carefully reviews safety data and immunogenicity data to evaluate the entry into phase 2.

The DSMB consists of the sponsor, the investigator of the laboratory, or its delegated person, and may include a clinical pharmacologist if necessary. Matters concerning the operation of the DSMB follow a separate plan.

15. OTHER MATTERS NECESSARY TO SAFELY AND SCIENTIFICALLY CONDUCT CLINICAL TRIALS

15.1 Clinical Trials Site

The head of a clinical trial site should equip the necessary facilities, professional manpower, and independent ethical institution for the execution of the relevant clinical trial at each stage of the

clinical trial, and make perfect preparations so that the relevant clinical trial can be properly carried out.

15.2 Principal Investigator and Clinical Site Staffs

The principal investigator and clinical site staffs should be fully aware of predicted adverse events and precautions for use through available information related to clinical investigational drugs, such as IB or drug attachments provided through the sponsor, and SAEs occurred during the clinical trial. In this case, the report shall be immediately reported to the Institutional Review Committee and the sponsor.

15.3 Protocol Violation

If it is known that the clinical trial protocol has been violated during the clinical trial, the investigator should notify the sponsor (or monitor) of the violation as soon as possible, and discuss and decide whether the subject continues to participate in the clinical trial.

In the case of dropout due to a serious clinical trial protocol violation (Section 4.4), all information collected up to the point of dropout and reasons for dropout should be collected in the eCRF.

15.4 Criteria for Treatment of Subjects after Clinical Trials

Treatment after the clinical trial for the subjects who dropped out of the clinical trial (Section 4.4) and those who completed the clinical trial should follow the general criteria for treatment and treatment.

However, if the subject is injured due to treatment or clinical procedures that would not have been received if they did not participate in this clinical trial, all treatments will be received according to the standard hospital procedures. Damage related to clinical trials will be borne by the sponsor in accordance with the sponsor's clinical trial victim compensation protocol and the terms and conditions of the sponsor's clinical trial compensation insurance.

1.1 Primary Objective – Phase I / IIa study

- Evaluate the safety and tolerability of GLS-5310 DNA vaccine
- Determine the binding antibody responses induced by GLS-5310 DNA vaccine relative to treatment arm

1.2 Secondary Objective – Phase I / IIa study

- Determine the T cell responses induced by GLS-5310 DNA vaccine
- Determine the neutralizing antibody response induced by GLS-5310

1.3 Exploratory Objective

Phase IIa Exploratory Objectives

- Determine the degree of immune response to GLS-5310 in participants under the age of 65 and those aged 66 to 85

2. Study Endpoints

2.1 Safety Endpoints

- Adverse Events (AEs)
- Vital signs
- Laboratory tests
- Assessment of Injection Site - The Solicited local AEs and Solicited Systemic AEs

2.2 Immunogenicity Endpoints

- Evaluation of GMT and serum conversion rates of SARS-CoV-2 Spike and ORF3a protein-specific binding antibodies induced by GLS-5310 (the end-point titer of binding antibodies in serum at each timepoint)
- Evaluation of GMT and positive responder rate of neutralizing antibody responses induced by GLS-5310 (plaque-reduction neutralizing titer, PRNT in serum at each timepoint)
- Evaluation of positive responder rate of T cell response induced by GLS-5310 (antigen-specific interferon – gamma (IFN- γ) secretion T-cell response in PBMC at each timepoint)

2.3 Exploratory Endpoints

2.3.1 Phase IIa Exploratory Endpoint

- Evaluation of the degree of immune response to GLS-5310 in subjects under 65 years of age and those aged 66 to 85 years of age

CONFIDENTIAL

3. Study Design

The Phase I / IIa study aims to evaluate the safety, tolerability and immunogenicity of GLS-5310 DNA vaccine.

The Phase I study is an open-label, dose escalation study. The Phase I study will assess two different dose levels of GLS-5310, LOW DOSE (0.6mg) and HIGH DOSE (1.2mg); two different vaccination schemas with vaccinations given ID at either 0 and 8 weeks or 0 and 12 weeks. GLS-5310 will be administered via intradermal (ID) injection using the Mantoux technique followed by suction applied over the vaccination site using the JM-11 device.

The Phase IIa study is designed as randomized, double-blind, placebo-controlled and will assess a single vaccination regimen with corresponding dose level chosen from the Phase I study. Randomization between Vaccine and Placebo arms will be in a 2:1 ratio. The study will be unblinded at the post-vaccination visit (Visit 4) at which time subjects will be informed of their treatment assignment. Subjects who were assigned to the placebo group will be offered to be vaccinated with GLS-5310 and will be followed for a year from 1st GLS-5310 vaccination. However, subjects assigned to the placebo group but who decline vaccination with GLS-5310 will be followed for a year from study entry as per the original study protocol.

4. Planned Analysis

4.1 Interim Analysis

Interim analyses were performed in stages.

- **Stage 1:** An assessment of AE's was performed after study Visit 1 for Group 1a.
- **Stage 2:** When all Phase I subjects (Groups 1a, 1b and 1c) had completed Visit 4, an interim analysis was performed to evaluate safety and antibody response.
In order for the study to move into Phase IIa study, the seroconversion rate for the binding antibody responses must be >70%. In addition, the incidence of Serious Adverse Events (Grade 3 or higher) related to the investigational product should be no more than 1 case.
- **Stage 3:** An interim analysis of Phase IIa study was performed after all patients complete their Visit 4. The purpose of this interim analysis was to provide options to placebo vaccinated subjects and to assess the safety of the vaccine after the second dose. For the interim analysis of Phase IIa, database locking was implemented before unblinding.

The study is unblinded at the post-vaccination visit (study Visit 4) at which time subjects are informed of their treatment assignment. Subjects who were assigned to the placebo group are offered to be vaccinated with GLS-5310. Subjects assigned to the placebo group who choose to be vaccinated with GLS-5310 are followed for a year from 1st GLS-5310 vaccination; subjects assigned to the placebo group but who decline vaccination with GLS-

CONFIDENTIAL

5310 are followed for a year from study entry as per the original study protocol.

5. Determination of Sample Size

This is an exploratory and descriptive Phase I/Ila clinical trial to evaluate the safety and immunogenicity of GLS-5310 for the purpose of preventing COVID-19, and dose not test statistical hypotheses, so the sample size is set within the limit of satisfying the research purpose. In the Phase I clinical trial, 45 subjects who meet the inclusion and exclusion criteria are registered to secure 15 subjects based on the allocation of each vaccination group. In the Phase Ila clinical trial, it is planned to secure 120 subjects based on randomization.

Randomization is performed 1:1 in 1b and 1c groups of Phase I clinical trial according to the planned random number, and 1:2 in placebo and vaccination groups in Phase Ila clinical trial to determine the difference between placebo and vaccination groups.

6. Analysis Sets

Safety and tolerability analyses will be performed on Safety Set.

✓ **Intention to treat (ITT)**

Intention to treat (ITT) will include all participants who sign informed consent.

✓ **Modified Intention to treat (mITT)**

Modified intention to treat (mITT) will include all participants who sign informed consent and who have received at least one administration of investigational product. The mITT will be the primary analysis population for baseline and demographic assessments and efficacy outcomes. All subjects will be summarized based on the treatment group to which they were assigned. Since not all subjects will have evaluable immune response data, analysis of immune responses will be performed only for available samples.

✓ **Safety Set (SS)**

Safety Set (SS) will include all mITT participants. The SS will be the primary population for summary and analysis of safety assessments. All subjects will be summarized based on the treatments that actually received.

✓ **Per-Protocol Set (PPS)**

Per-Protocol Set (PPS) will include all mITT participants who complete the trial by receiving all

CONFIDENTIAL

vaccinations and have no significant protocol violations. This set will be used as a sensitivity analysis to summarize the primary and secondary response outcomes. For secondary and exploratory assessments of antibody and T cell immune responses, denominators will include only those participants who are SARS-CoV-2 seronegative at baseline. Unevaluable samples will not be considered as part of the denominator at relevant time points.

Protocol violations that can be excluded from the analysis group include the following and are defined according to the analysis population's definition of 'SOP 0406'.

- Participants who have never been vaccinated with all vaccinations
- Positive for SARS-CoV-2 serum test at Baseline
- Inclusion/Exclusion criteria violation
- Contraindicated drug administration
- Randomization errors
- Vaccination errors
- No blood draw for immunogenicity assessment

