6.1 Errors in Investigational Product Vaccination

If a subject was not administered with the investigational product that was randomized (planned), the subject will be analyzed according to the following rule:

- If the wrong treatment was used for the entire trial, then he/she will be analyzed according to the actual treatment group for the safety analyses and randomized treatment group for the immunogenicity analyses complying to the intent-to-treat (ITT) principle.
- If the wrong treatment was used for only one of the vaccinations, he/she will be grouped into the highest dose (1.2 mg in Phase I, or treatment arm in Phase IIa) for safety and in the randomized arm for the immunogenicity analyses.

7. General Analysis Considerations

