8.2 Handling of Missing Data

If there are missing dates and are used in calculations, they will be imputed as the following:

Table 1 Handling of missing or partial date

Types of Dates	Missing	Imputation	Examples
Prior/ Concomitant medication start date	YYYY-MM-DD	Year of the date of informed consent-01(January)-01	Date of informed consent: 2018-12-05 Collected date: UK-UK-UK Imputed date: 2018-01-01

CONFIDENTIAL

Types of Dates	Missing	Imputation	Examples
	MM-DD	01(January)-01	Collected date: 2018-UK-UK Imputed date: 2018-01-01
	DD	01	Collected date: 2018-12-UK Imputed date: 2018-12-01
Prior/ Concomitant medication end date	YYYY-MM-DD	Final visit date	Final visit date: 2018-12-25 Collected date: UK-UK-UK Imputed date: 2018-12-25
	MM-DD	12-31	Collected date: 2018-UK-UK Imputed date: 2018-12-31
	DD	Last day of the month	Collected date: 2018-12-UK Imputed date: 2018-12-31
AE start date	YYYY-MM-DD	First IP administration date	Date of first IP administration: 2018-12-05 Collected date: UK-UK-UK Imputed date: 2018-12-05
	MM-DD	1. The year of the IP administration date = The year of the AE start date: The month and day of the IP administration date 2. The year of the IP administration date ≠ The year of the AE start date: 01-01	1. Date of IP administration: 2018-12-05 Collected date: 2018-UK-UK Imputed date: 2018-12-05 2. Date of IP administration: 2018-12-05 Collected date: 2019-UK-UK Imputed date: 2019-01-01
	DD	1. The year and the month of the IP administration date = The year and the month of the AE start date: The day of the IP administration date 2. The year and the month of the IP administration date ≠ The year and the month of the AE start date: 01	1. Date of IP administration: 2018-12-05 Collected date: 2018-12-UK Imputed date: 2018-12-05 2. Date of IP administration: 2018-12-05 Collected date: 2019-05-UK Imputed date: 2019-05-01
AE end date	YYYY-MM-DD	1. If the subject is dead: Death date 2. If the subject is not dead and has date of the last observation/date of early termination: Last observation/date of early termination	1. Death date: 2018-12-30 Collected date: UK-UK-UK Imputed date: 2018-12-30 2. Last observation/early termination date: 2018-12-30 Collected date: UK-UK-UK Imputed date: 2018-12-30

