8.4 Derived or transformed variables

The baseline is defined as last non-missing value on or prior to the start date of IP administration.

Table 4 Derived Variables

Variables	Method
Change from baseline	Post-baseline value – Baseline value
Age group	Age < 66y old, Age \geq 66y old
Total dose (mg)	Sum of investigational product doses at each time point
GMT	$10^{\text{Mean of log}_{10} \text{ value}}$

CONFIDENTIAL

Variables	Method
Change from baseline (GMT)	$10^{(\text{Mean of } (\log_{10} \text{post} - \text{baseline value} - \log_{10} \text{baseline value}))}$
GMR	$10^{(\log_{10} \text{GMT1} - \log_{10} \text{GMT2})}$
AE Duration (days)	AE end date – AE start date+1 if AE end date is ongoing, replaced with last visit date and add symbol (\geq) (ex. ≥ 15)
Occurrence Duration (days)	AE start date – Investigational product start date

9. Subject Information

Subject information will be analyzed on ITT.

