10.2 Adverse Events

An adverse event (AE) is defined as any unfavorable and unintended change in the structure, function, or chemistry of the body, or worsening of a pre-existing condition, temporally associated with the use of a product whether or not considered related to the use of the product.

Frequencies will be presented with respect to maximum severity and to strongest relationship to vaccination of the investigational product. Multiple occurrences of the same AE will be counted only once following a worst-case approach with respect to severity and relationship to vaccination of the investigational product.

Treatment-emergency adverse event (TEAE) refers to any AE that did not exist prior to vaccination of the investigational product, but that occurred after the initial vaccination of the investigational product, or a pre-existing condition that worsens after the initial vaccination of the investigational product.

Adverse drug reaction (ADR) is any noxious and unintended response to a medicinal product related to any dose, which a causal relationship between a medicinal product and an adverse event cannot be ruled out. An ADR includes reactions that represent an unexpected worsening of an existing medical condition. The following relationship categories will be considered as ADR:

- Probably related
- Possibly related

CONFIDENTIAL

A serious adverse event (SAE) is any AE that meets one of the following conditions:

- Death
- Life-threatening events
- An event requiring inpatient hospitalization or prolongation of existing hospitalization during the period of protocol defined surveillance (including any overnight stay in the hospital, regardless of the length of stay, even if the hospitalization is only a precautionary measure to allow continued observation).
NOTE: Evaluation in a physician's office, or at a hospital or other urgent care setting in an observational, non-admitted status regardless of the time period of observation, does not constitute an SAE
- Events resulting in congenital anomaly or birth defect
- Events that cause persistent or significant disability/incapacity or substantial disruption of the ability to conduct normal life functions
- Other important medical events that may not result in death, are life threatening, or require hospitalization, but are considered as serious by the Investigator. Examples of such medical events include anaphylaxis, new onset seizures

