10.2.2 Analysis Adverse Events

The following types of AEs will be coded with medical dictionary for regulatory activities (MedDRA) version 25.0 and will be summarized with system organ class (SOC) and preferred term (PT) by vaccination group using number of subjects, percentages, and number of events.

- TEAEs
- ADRs
- All Serious TEAEs
- Serious adverse drug reaction (SADR)
- All TEAEs leading to vaccination discontinuation
- Adverse Events of Special Interest
- TEAEs by severity (toxicity grade)
- ADRs by severity (toxicity grade)
- TEAEs by relationship to the investigational product
- Solicited local TEAEs
- Solicited local ADRs
- Solicited local SAEs
- Solicited local SADR
- Solicited systemic TEAEs
- Solicited systemic ADRs
- Solicited systemic SAEs
- Solicited systemic SADR

The details of SAEs will also be presented in a listing.

CONFIDENTIAL

The details of Solicited local/systemic SAEs will also be presented in a listing.

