10.3 VAS Scores

VAS score will be summarized by each timepoint using number of subjects, mean, standard deviation, median, minimum, and maximum by vaccination group.

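### No adverse-event table specified in the SAP is by dose, so the tables do not show the safety after the second dose that Stage 3 was to assess

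*SAP*

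**What the plan says.** SAP 4.1 gives Stage 3 two purposes. One is to give placebo participants their options. The other is "to assess the safety of the vaccine after the second dose". The timing of the analysis, once everyone has completed Visit 4, is stated separately.

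The SAP then specifies AE output as follows.

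- **Layout (10.2.1, 10.2.2).** Tables are by system organ class and preferred term, "by vaccination group using number of subjects, percentages, and number of events". The further breakdowns are by seriousness, severity, relationship, discontinuation, special interest and solicited local or systemic type. None is by dose number or by time since the last dose.
- **Counting (10.2).** "Multiple occurrences of the same AE will be counted only once following a worst-case approach".
- **Onset (8.4, Table 4).** The only onset variable is "AE start date – Investigational product start date".
- **Missing dates (8.2, Table 1).** A wholly missing AE start date is set to "First IP administration date".
- **Denominator (section 6).** The Safety Set is everyone in the mITT set, that is, anyone with at least one administration.

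Other safety data are handled differently. "VAS score will be summarized by each timepoint" (SAP 10.3), and SAP 10.4 and 10.5 treat laboratory values and vital signs the same way.

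Protocol 11.3.1 bases the main interim safety summary on events within 28 days of administration. Protocol 7.3.3 has participants complete a diary for 7 days after each vaccination.

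**The concern.** Safety and tolerability is a primary objective of both phases. For a two-dose vaccine, an obvious question is whether reactions become more or less frequent, or more or less severe, at the second dose. SAP 4.1 asks about safety after that dose, but the AE tables in section 10 do not report it.

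The 28-day window, the one element of the protocol's safety analysis that is anchored to an administration, does not appear in SAP section 10. SAP section 12, which records changes from the protocol, does not mention it.

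Phase I has a secondary consequence. Arms 1b and 1c receive the same first dose (1.2 mg) and differ in when the second is given. Protocol 3.1 says that AEs at the Visit 4 interim analysis help to choose the regimen. An any-dose table mixes the part of the experience that could differ with a part that should not.

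**Working it through.** The documents give no AE rate by dose and no figure to reproduce here. The rates below are assumptions that show what an any-dose table can and cannot reveal.

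**1. Can the dose-2 rate be read from the any-dose incidence?** Let p1 and p2 be the proportions with a given reaction after dose 1 and after dose 2. If the doses are independent, any-dose incidence = 1 − (1 − p1)(1 − p2).

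- p1 = 40%, p2 = 20%: 1 − 0.6 × 0.8 = 52%.
- p1 = 20%, p2 = 40%: 1 − 0.8 × 0.6 = 52%.

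One vaccine is half as reactogenic at dose 2 and the other twice, yet the table entry is the same. The event count does not separate them either: with at most one event per dose, both average 0.4 + 0.2 = 0.6 events per participant.

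Independence is not essential. In general, any = p1 + p2 − both, so p2 lies between (any − p1) and any. For an any-dose incidence of 60%:

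| Dose-1 rate | Possible dose-2 rate | Dose-2 rate if independent |
|---|---|---|
| 50% | 10% to 60% | 1 − 0.4/0.5 = 20% |
| 20% | 40% to 60% | 1 − 0.4/0.8 = 50% |
| not reported | 0% to 60% | – |

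The planned tables are in the last row.

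**2. Does the onset variable help?** Visit 3 is planned for day 56 in the 0–8 week schedule and day 84 in the 0–12 week schedule (SAP Tables 2 and 3). A reaction on the day after dose 2 therefore has onset 57 or 85. A reader of listings can work out the dose, but the variable does not put reactions to the two doses on one scale, and no table uses it to separate them.

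**3. Does the denominator help?** If a fraction d of the Safety Set never receives dose 2, a dose-2 rate taken over that set is (1 − d) times the rate among recipients. No dose-2 denominator is defined.

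**4. Arms 1b and 1c.** Let q be the shared dose-1 incidence. Under independence, the any-dose difference = (1 − q) × the dose-2 difference. With assumed dose-2 rates of 50% and 20%, the 30-point difference appears as:

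- q = 0: 30 points
- q = 0.2: 24 points
- q = 0.4: 18 points
- q = 0.6: 12 points

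For scale, the widest 95% half-width for a difference between two arms of 15 is 1.96 × √(0.5/15) = 0.358, about 36 points. Imprecision outweighs the dilution.

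**5. Which windows allow a fair comparison?** Open-ended windows would not. Dose 1 to dose 2 lasts 8 weeks in 1b and 12 in 1c. Dose 2 to Week 48 lasts 40 weeks and 36. The protocol's 7-day and 28-day windows are equal in both arms, and a 28-day window after dose 1 closes before the earliest permitted second dose (day 53).

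**The case against.** The strongest reply is that the information exists. AE start dates are recorded, diaries are kept for each vaccination, listings are planned, and VAS, laboratory and vital-sign summaries already separate the doses by timepoint. This stands. A reader might infer that the SAP has no by-dose safety output, or that its rules erase the dose an event followed. Neither is supported. The count-once rule governs counting, not the data. The default to the first dose applies only to wholly missing dates. The rule beginning "If the wrong treatment was used for only one of the vaccinations, he/she will be grouped into the highest dose" applies only to vaccination errors. The gap is confined to AE and solicited-reaction tables.

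A reader might also infer that Stage 3 could not achieve its purpose. That goes too far. SAP 4.1 reports Stage 3 in the past tense, a different SAP version may have governed it, and the table shells (section 18) are not in the text available. The phrase about the second dose could also describe only when the data were cut. That reading is possible but less natural, because the timing is already given in the preceding sentence. Section 10 is written prospectively, so the remaining tables can still be specified properly.

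It is tempting to turn the dilution in 1b and 1c into a loss of power. The documents do not support that. SAP 10.2.1 plans AE differences for Phase IIa only, and SAP section 5 says the trial tests no hypotheses. Under the assumed 50% and 20%, exact Fisher power at two-sided 5% would be only 25% even for dose 2 alone. The Phase I comparison is descriptive, and no power claim is made.

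Finally, any-dose incidence is a legitimate overall summary, and no listed endpoint is defined by dose. Both are true, which limits the severity. Neither supplies the assessment named in SAP 4.1.

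**Conclusion.** The point holds for AEs and solicited reactions. As specified, the SAP's AE tables do not show the reaction rate after the second dose, although SAP 4.1 names safety after that dose as a purpose of Stage 3. The protocol's 28-day window has also dropped out of SAP section 10 unrecorded.

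The size depends on unknown rates. An any-dose incidence of 60% is compatible with a dose-2 rate anywhere from 0% to 60%; this needs no independence assumption. The 52% example and the (1 − q) factor do assume independent doses, and (1 − q) also assumes the same dose-1 incidence in 1b and 1c. That factor affects only a descriptive side-by-side reading with 15 per arm.

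Nothing here biases the any-dose comparison of vaccine with placebo. The change should be made, but its absence does not invalidate the safety analysis. If the shells already split AEs by dose, the remaining task is to say so in the SAP text.

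**What to change.** 1. In SAP 10.2.1–10.2.2, add tables after dose 1 and after dose 2, by arm and maximum grade: solicited local and solicited systemic reactions over the protocol's 7-day diary window, and treatment-emergent AEs over its 28-day window.
2. Use participants who received that dose as the denominator, and apply the count-once rule within each dose.
3. In Table 4, add onset in days from the most recent vaccination. Flag events whose start date was imputed, because a wholly missing date is assigned to dose 1 by default.
4. Keep the any-dose table as the overall summary.
5. If the 28-day window was dropped on purpose, record that in section 12 with the reason.

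The visit windows in SAP Table 2 allow Visit 4 to fall 22 to 34 days after dose 2 (81 − 59 and 87 − 53). Tables cut at Visit 4 should therefore state how many participants had not completed the 28 days.

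The cost is SAP wording and a few extra tables from data already collected. There are no new procedures or visits.
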